## 10.6 Study Duration

Study duration will be calculated as,

Study Duration (days) = (Date of EOS / Early Termination visit – Date of Informed Consent) + 1.

## 10.7 Migraine History

Time since migraine diagnosis (years) = (Informed consent date – date of migraine diagnosis)+1/365.25.

## 10.8 Medical History and Concurrent Diseases

Medical history with an end date prior to Visit 2 will be considered as medical history.

Medical history with missing end date or ongoing during Visit 2 will be considered as concurrent diseases. Adverse events occurring after Visit 2 and before IMP (Period 1) will also be flagged in the analysis datasets and summarised as concurrent diseases.

## 10.9 Prior and Concomitant Medications

Medications will be summarised by the study periods below: •

Prior: Pre-Day 1

- Concomitant:
  - Pre-IMP
  - Post-IMP: LAT8881 60 mg and Placebo

Study Period	Rule
Prior	Medications that started and ended before Visit 2.
Pre-IMP	Medications that are ongoing on or after Visit 2 but before any dose of IMP (LAT8881 or placebo) irrespective of study periods.
Post-IMP: LAT8881 60 mg and Placebo	
Period 1: Medications that are ongoing on or after dose of IMP (LAT8881 or placebo) in period 1 but before IMP in period 2.
 
Period 2: Medications that are ongoing on or after dose of IMP (LAT8881 or placebo) in period 2.

If a subject has ongoing medication in more than one study period, then the use of that medication will be counted in all applicable study periods. New medications added in the corresponding study period and medications that are ongoing from the previous study period will be flagged and summarised separately within each study treatment.

If the medication is started on the same day of IMP dosing, but timing of onset of event in relation to IMP dosing is not clear, then, the worst case will be considered (Post-IMP). This will also be raised to

the site and if this is confirmed to be before dose then a note to file (NTF) will be created stating the same. This will be incorporated into the analysis datasets for analysis purposes.

### 10.10 Adverse Event Flags

Adverse events will be summarised by the study periods below and flags generated:

- Pre-IMP
- Post-IMP: LAT8881 60 mg
- Post-IMP: Placebo

Study Period	Rule
Pre-IMP	AEs started before any dose of IMP (LAT8881 or placebo) irrespective of periods.
Post-IMP: LAT8881 60 mg and Placebo	
Period 1: AEs that started on or after dose of IMP (LAT8881 or placebo) in period 1 but before IMP in period 2.
 
Period 2: AEs that started on or after dose of IMP (LAT8881 or placebo) in period 2.

An additional flag will be generated for treatment emergent adverse events (TEAE) if they occurred or worsened on or after the first administration of IMP (LAT8881 or placebo) irrespective of the study period. Adverse events occurring prior to first dose of IMP (LAT8881 or placebo) will not be considered as TEAEs. For example, for subjects who had taken the IMP in period 1, any AE post that dose will be considered as a TEAE regardless of whether it is before or after the dose of IMP in period 2. For subjects who had taken their first dose of IMP in period 2, i.e. did not take IMP during period 1, any AEs post IMP in period 2 will be considered as TEAEs.

If an adverse event occurred in a study period and continues to other study periods, it will be counted in all the applicable study periods. New events occurred in the corresponding study period and events that are ongoing from the previous study period will be flagged and summarised separately within each study treatment.

AEs that are ongoing from the previous period but just change in severity will still be considered as an ongoing AE. This will be identified and manually flagged during the blinded review meeting. AEs that are resolved and restart will be considered as a new event.

If the event occurs on the same day of IMP dosing, but timing of onset of event in relation to IMP dosing is not clear, then, worst case will be considered (Post-IMP). This will also be raised to the site and if this is confirmed to be before dose then a note to file (NTF) will be created stating the same. This will be incorporated into the analysis datasets for analysis purposes.

Related Adverse Events will be flagged for Possibly, Probably and Definitely Related adverse events.

All related SAEs will be considered Suspected unexpected serious adverse events (SUSARs) and included in analyses datasets.

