13.1 Definitions

13.1.1 Adverse event

An adverse event is any untoward medical occurrence in a patient or clinical investigation subject administered a pharmaceutical product and may not necessarily have a causal relationship with the administered treatment.

An AE can therefore be any unfavourable and unintended sign (including an abnormal laboratory finding), symptom, or disease temporally associated with the use of a medicinal (investigational) product, whether or not it is related to the medicinal (investigational) product. This includes an exacerbation of pre-existing conditions or events, intercurrent illnesses, drug interaction or any worsening (ie any clinically significant adverse change in frequency and/or intensity) of a pre-existing condition, which is temporally associated with the use of the sponsor's product. Anticipated fluctuations of pre-existing conditions, including the disease under study, that do not represent a clinically significant exacerbation or worsening need not be considered AEs.

Laboratory reference ranges are defined by upper or lower limits of parameters of the respective laboratory. The investigator should ensure that each parameter out of the normal range is assessed for clinical significance and the potential for being an AE (refer to Section 13.3). An adverse event is defined as 'serious' when it meets one of the pre-defined outcomes as described in Section 13.1.6.

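### The per-treatment AE tables cannot separate an event that worsened after the second dose from one that carried over unchanged

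*SAP*

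**What the plan says.** SAP 10.10 (Adverse Event Flags) sets two separate flags.

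- **TEAE flag.** An event qualifies "if they occurred or worsened on or after the first administration of IMP (LAT8881 or placebo) irrespective of the study period". For a subject dosed in Period 1, the section adds that "any AE post that dose will be considered as a TEAE regardless" of its timing relative to the Period 2 dose.
- **New or ongoing status.** An event present in one period that "continues to other study periods, it will be counted in all the applicable study periods", and "events that are ongoing from the previous study period will be flagged and summarised separately within each study treatment". If only the grade changes, the status does not: "AEs that are ongoing from the previous period but just change in severity will still be considered as an ongoing AE". An event becomes new only if it stops and comes back. On the events whose grade changes, the section says "This will be identified and manually flagged during the blinded review meeting".

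The rule in 10.10 that assigns events to the Period 2 treatment uses the start date alone and does not mention worsening.

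The TEAE tables in SAP 11.9.1.1 and 11.9.1.2 use two statuses, new and ongoing, by treatment and period. SAP 11.9.1.3 tabulates Grades 1 to 5 by treatment and period. Protocol 13.1.1 includes in its definition of an adverse event "any worsening (ie any clinically significant adverse change in frequency and/or intensity) of a pre-existing condition".

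**The concern.** In a crossover, the Period 2 dose is the subject's first exposure to the other treatment. A rise in grade after that dose is the kind of change that a safety comparison between LAT8881 and placebo should be able to show. The plan accepts worsening as emergent relative to the first dose, yet gives it no place in the status tables relative to the second. The treatment taken second can therefore have post-dose worsening that no row of its own table identifies.

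Safety and tolerability are a stated secondary objective (Protocol 4.2), and with about 20 subjects per treatment a single such case is worth seeing. The situation can arise: Protocol 5.2 requires only 48 hours between doses, so an event can span both.

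**Working it through.** The plan gives no figure to reproduce, so the check traces its counting rules and then gives a range for size.

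**Step 1: the two rules side by side.** The TEAE flag asks whether the event occurred or worsened after the *first* dose. The status flag asks whether the event started in this period or the previous one. Worsening enters the first question but not the second, and no rule asks whether an event worsened after the *second* dose.

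**Step 2: trace two events.** Both start at Grade 1 after dose 1 and are still present at dose 2. One stays at Grade 1; the other reaches Grade 3 after dose 2.

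| Event | TEAE | Period 1 treatment, new | Period 2 treatment, new | Period 2 treatment, ongoing |
|---|---|---|---|---|
| Unchanged after dose 2 | yes | 1 | 0 | 1 |
| Grade 3 after dose 2 | yes | 1 | 0 | 1 |

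The rows are identical, so the new/ongoing tables cannot tell the events apart.

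**Step 3: can the severity table recover it?** Only if each period uses the grade reached in that period, and SAP 11.9.1.3 does not say so. Protocol 13.2 requires start and stop dates and intensity for each event, but no date of grade change. If the data hold one grade per event, and the event is counted in both periods, a Grade 3 reached only after dose 2 could also be tabulated under the Period 1 treatment. The documents do not settle this either way.

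**Step 4: can the manual flag recover it?** SAP 10.10 provides for these cases to be identified at blinded review, but neither 10.10 nor 11.9.1 assigns the flag to a table or listing.

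**Step 5: size.** Only subjects dosed in both periods can be affected. The planned number of completers is n = 20 (Protocol 5.4, SAP 4.2). Let q be the chance that a subject has a carried-over event that worsens after dose 2. The documents give no value, so q is assumed over a range. Expected cases are n × q, and the chance of at least one is 1 − (1 − q)^n.

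- q = 1%: 20 × 0.01 = 0.2 cases; 1 − 0.99^20 = 18%.
- q = 5%: 20 × 0.05 = 1.0 case; 1 − 0.95^20 = 64%.
- q = 10%: 20 × 0.10 = 2.0 cases; 1 − 0.90^20 = 88%.

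With 10 completers per sequence (assumed, since the allocation ratio is not stated), each treatment would have 0.1, 0.5 or 1.0 of these cases.

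**The case against.** A reader might infer that the severity rule contradicts the TEAE definition. It does not. That definition is anchored to the first dose, irrespective of period, and the traced event is a TEAE from its onset and stays one. New or ongoing is a different flag. Even on the first-dose side, the sentence that follows the TEAE definition excludes pre-dose events and makes no exception for worsening, so the wording there also needs tidying.

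A reader might also take Protocol 13.1.1 as being breached. That section defines what has to be recorded as an adverse event. It does not say how a recorded event is labelled across crossover periods.

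The strongest point on the other side is that nothing is removed from the second treatment's tables. The event is counted there as ongoing, it appears in the by-subject listing, and if it becomes serious it is also reported and listed as an SAE. The data display plan cited in SAP 12, which might show more, is not available here. All of this stands, and it rules out any claim that harm is hidden. It does not answer the narrower point: under the written rules, no status row shows that the event got worse after that dose.

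It can also be objected that counting the worsened event as new would make one continuous event new under both treatments and inflate event counts. That is correct, and it is why the fix uses a separate status.

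**Conclusion.** The point holds as a gap in display and counting. SAP 10.10 treats worsening as emergent after the first dose but leaves worsening after the second dose indistinguishable from an unchanged carry-over, and 11.9.1.3 does not say which grade belongs to which period. The number of subjects with a TEAE does not change.

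The rule has no built-in direction, because either treatment can come second. If one treatment did worsen carried-over events more often, the new-event comparison would miss those cases.

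The size is unknown. The range of 0.2 to 2 expected cases rests on 20 completers and an assumed 1% to 10% chance per subject. A reader might infer a distortion of 4 to 5 percentage points in a new-event rate. That is only the weight of one subject (1/25 to 1/20). It applies only if such a case occurs and the subject has no other new event on that treatment, and the documents offer no frequency to support it. This is a cheap improvement to the plan; it does not invalidate the safety analysis.

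**What to change.** 1. In SAP 10.10, give an event that is ongoing at the Period 2 dose, and whose grade increases on or after that dose, its own status: 'ongoing, worsened after this dose'. Events with an unchanged or lower grade stay ongoing.
2. In the 11.9.1.1 and 11.9.1.2 tables, summarise that status under the Period 2 treatment, next to the new events.
3. In 11.9.1.3, tabulate the maximum grade reached within each period under that period's treatment.
4. Confirm that the date of a grade change is captured, so that it can be placed before or after the Period 2 dose.

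The cost is one extra row or status in the tables and one data item to confirm. SAP 10.10 already has these events identified at the blinded review meeting, so the first three steps need only a change of SAP wording before database lock. The fourth may need a query to the site if the date was not collected.

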10.3 Safety endpoints

1. Changes in physical examinations and vital signs
2. Changes in clinical laboratory tests
3. Percentage of Treatment emergent adverse events (TEAEs), including serious adverse events (SAEs), and suspected unexpected serious adverse reactions (SUSARs)
4. Changes in concomitant medications

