13.1.3 Suspected unexpected serious adverse reactions

Suspected unexpected serious adverse reactions (SUSARs) are AEs that are believed to be related to an IMP and are both unexpected (ie the nature or intensity is not expected from the information provided in the Investigator's Brochure) and serious. SUSARs are subject to expedited reporting to the applicable regulatory authorities.

For regulatory reporting purposes, SUSARS will be unblinded.

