13.4 Reporting of serious adverse events

Any SAE must be reported by the investigator if it occurs during the clinical study or within 2 weeks of the subject having received the last dose of IMP, whether or not the SAE is considered to be related to the IMP. This shall include pregnancy in a female subject or in a female partner of a male study subject. Instances of death, congenital abnormality or an event that is of such clinical concern as to influence the overall assessment of safety, if brought to the attention of the investigator at any time after cessation of IMP administration and linked by the investigator to this study, should be reported to the sponsor.

The investigator must report an SAE on an SAE report form and forward the SAE report form, the AE form and the concomitant medication form to the sponsor or delegate **within 24 hours of becoming aware of the SAE** and **regardless of causality**. All pregnancies in a female subject or in a female partner of a male study subject should be reported on a Pregnancy report form following the same reporting process and timelines required for SAEs.

The investigator should not wait to receive additional information to document fully the event before notification of a SAE, though additional information may be requested. Where applicable, information from relevant laboratory results, hospital case records and autopsy reports should be obtained.

Followup information on SAEs must also be reported by the investigational site to the sponsor within the same time frame. If a non-serious AE becomes serious, this and other relevant followup information must also be provided within 24 hours of the investigator becoming aware.

All SAEs will be recorded in the subject's source documents and the CRF.

It is the responsibility of the sponsor to determine whether a reported SAE fits the classification of a SUSAR (refer to Section 13.1.3). If the sponsor considers the SAE to be drug related (ie an adverse drug

reaction), unexpected and fulfils the criteria for a suspected unexpected serious adverse reaction (SUSAR), the sponsor has the responsibility to expedite the reporting to all concerned investigators, to the EC where required, and to the appropriate regulatory authorities within the pre-defined timelines.

The investigator must notify their EC of SAEs occurring at the site, within the time period and in accordance with requirements specified by the EC.

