#### **11.9.1.1 Overall Adverse Events**

The number and percentage of subjects and number of events will be summarised by AE status (new event or ongoing from the previous study period), treatment overall and within each study period for the following categories:

1. All adverse events reported
2. Treatment emergent adverse events (TEAEs)
3. Serious adverse events
4. Serious treatment-emergent adverse events
5. Related treatment-emergent adverse events
6. Related treatment-emergent serious adverse events
7. Suspected unexpected serious adverse events (SUSARs)
8. Treatment-emergent adverse events leading to death
9. Treatment-emergent adverse events leading to study discontinuation

The above categories and study periods will be classified as defined in section 10.10.

In DDP: Table 14.3.1.1 and Table 14.3.1.2

All adverse events will be listed by subject, system organ class and preferred term sorted by event start dates. Serious adverse events and deaths due to adverse events will be listed separately.

In DDP: Listing 16.2.7.1 to 16.2.7.3

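### SAP 10.10 flags every related SAE as a SUSAR without the protocol's test of unexpectedness, so the SUSAR row is mis-defined and could over-count

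*SAP*

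**What the plan says.** SAP 10.10 sets two rules in succession. The first defines relatedness broadly: "Related Adverse Events will be flagged for Possibly, Probably and Definitely Related adverse events". The second builds the SUSAR flag on it: "All related SAEs will be considered Suspected unexpected serious adverse events (SUSARs"). Under these rules an event needs only to be serious and at least possibly related.

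Protocol 13.1.3 defines the term differently. SUSARs "are AEs that are believed to be related to an IMP and are both unexpected (ie the nature or intensity is not expected" on the information in the Investigator's Brochure, and they must also be serious. Protocol 13.4 names unexpectedness again as a condition and says who decides: "It is the responsibility of the sponsor to determine whether a reported SAE fits the classification of a SUSAR".

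The flag reaches a reported table. SAP 11.9.1.1 lists nine categories for the overall adverse event summary. Category 6 is "Related treatment-emergent serious adverse events" and category 7 is SUSARs. The section says that its categories are classified as defined in SAP 10.10. Safety endpoint 3, in Protocol 10.3 and SAP 7.3, is the percentage of treatment-emergent adverse events and includes "suspected unexpected serious adverse reactions (SUSARs").

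**The concern.** The SAP keeps the protocol's term but drops one of its three conditions and the link to the sponsor's decision. Nothing else in the SAP restores either. SAP 8.1, which lists changes to the planned analyses, does not mention a new SUSAR definition. Nor does the sentence read as a deliberate conservative default: where SAP 10.10 intends one, for events with unclear timing relative to dosing, it says that the worst case is taken.

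At stake is the meaning of one row in the safety overview. A reader of the study report will take SUSAR in the protocol's sense, in which the event was unexpected and went through expedited reporting with unblinding. An expected related SAE in that row would imply regulatory steps that the protocol did not call for. The row also gives no information beyond the one above it, although the table treats the two as separate concepts.

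**Working it through.** The plan gives no figure to reproduce here. The check compares definitions and then applies a counting identity.

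**Step 1. Conditions side by side.**

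| Condition | Protocol 13.1.3 and 13.4 | SAP 10.10 |
|---|---|---|
| Serious | required | required |
| Related to IMP | required; the sponsor's view (13.4) | required; possibly, probably or definitely related |
| Unexpected against the Investigator's Brochure | required | absent |
| Who classifies | the sponsor (13.4) | automatic from the flag |

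**Step 2. Effect on the count.** Let K be the number of related SAEs and E the number of those that are expected according to the brochure, with 0 ≤ E ≤ K. Assume for now that the sponsor and the flag agree on causality.

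- SAP rule: SUSAR count = K
- Protocol rule: SUSAR count = K − E
- Difference = K − (K − E) = E

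| K | SAP count | Possible protocol counts (E = 0, 1, …, K) |
|---|---|---|
| 0 | 0 | 0 |
| 1 | 1 | 1, 0 |
| 2 | 2 | 2, 1, 0 |

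On expectedness the SAP rule can over-count but cannot under-count. When E = 0 the two rules agree.

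**Step 3. Overlap of the two rows.** Category 6 is limited to treatment-emergent events; the SUSAR rule in SAP 10.10 is not. They are therefore not identical by definition. A related SAE can hardly precede the first dose, however, so in practice category 7 repeats category 6.

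**Step 4. A second route to a difference.** Under Protocol 13.1.4 the investigator assigns causality to each event. Protocol 13.4 rests the SUSAR decision on whether the sponsor considers the event drug related. If the SAP flag uses the recorded category, it can differ from the sponsor's decision even when E = 0. By this route the difference could go in either direction.

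**Step 5. Likely size.** The documents give neither a related-SAE rate nor the brochure's list of expected reactions, so any probability rests on assumption. For illustration only, let r be the related-SAE rate per dose and s the share of those events that are expected. With 26 subjects × 2 doses = 52 doses, the chance of at least one wrongly labelled event is 1 − (1 − r·s)^52.

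| Assumed r | s = 0 | s = 25% | s = 100% |
|---|---|---|---|
| 0.1% | 0% | 1.3% | 5.1% |
| 1% | 0% | 12% | 41% |

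The spread shows that the answer is set by the assumptions. It does not support any particular estimate.

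**The case against.** The strongest reply is that the gap may never change a number. If the brochure lists no serious reaction as expected, every related SAE is unexpected and the counts agree. The visible text leans that way. Protocol 3.2 reports no significant safety issues in the earlier programme. Protocol 3.2.2 describes the drug as well tolerated, with a single dose-related trend that later studies did not show. This stands as a limit on the consequence, but it does not mend the definition, which should not depend on whether events occur.

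The effect is also narrow. Related serious treatment-emergent events keep their own correctly labelled row, and SAEs are listed separately, so no event is lost. SUSARs are a component of safety endpoint 3 and not an endpoint in their own right, and the adverse event summaries planned in Protocol 14.6.2 include no SUSAR row; the SAP adds it. All of this stands.

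A reader might infer more: that the SUSAR result is certain to be misreported, that the study report is bound to contradict the sponsor's expedited reports, or that expedited reporting itself is at risk. The documents do not support this. The first two depend on at least one related SAE being expected, or on the sponsor's causality view differing from the flag, and neither can be known from the documents. The third fails because expedited reporting runs through the sponsor's process in Protocol 13.4, not through an analysis flag.

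Finally, the repair needs some care. The data items that Protocol 13.2 requires for each adverse event do not include expectedness, so the classification has to be brought in from the sponsor's safety records. Protocol 13.1.3 has SUSARs unblinded for regulatory reporting, while Protocol 8.1.2 withholds the randomisation schedule until the database is locked. The transfer must not carry allocation with it. This point is right and shapes the fix.

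**Conclusion.** Wrong as written, with minor impact. SAP 10.10 contradicts Protocol 13.1.3 and 13.4 by omitting unexpectedness, and Protocol 13.4 by bypassing the sponsor's determination. The SUSAR row in SAP 11.9.1.1 is mis-defined whatever events occur. Its count is too high by E, the number of related SAEs that are expected, provided that the sponsor and the flag agree on causality. E cannot be determined from the documents and may be zero in a trial of about 26 subjects. Efficacy results, the related-SAE row and expedited reporting are not affected.

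**What to change.** Replace the SUSAR sentence in SAP 10.10 with: *SUSARs are SAEs that the sponsor has classified as related and unexpected against the Investigator's Brochure (Protocol 13.1.3, 13.4); the classification, without treatment allocation, is added to the analysis dataset.* Keep related serious treatment-emergent events as their own row in SAP 11.9.1.1. In the same edit, call these events reactions in both sections, to match the protocol and the SAP's own abbreviation list.

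If the broad rule is intended, relabel the row as related SAEs and declare the change in SAP 8.1.

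The first option costs one sentence and the transfer of one variable. Protocol 13.4 already obliges the sponsor to make the classification, but no section shows that it reaches the analysis database, so that transfer has to be arranged. The second option needs no new data.
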